2.3.3 Rationale for immunobiologic endpoints

The major efficacy goal of this study is to assess a decrease in M2-TAM infiltration in tumors based on our preliminary data. To do this, we have developed a CD206 antibody for immunohistochemical analysis (IHC) and demonstration of M2-TAM infiltration into primary and metastatic prostate cancers. The analysis of M2-TAM infiltration into human tumors has previously not been possible because of lack of a specific marker for M2 macrophages. Current markers, e.g., CD68, are specific for all human macrophages but do not reflect polarization states. Working with our collaborator [name], Director of the Tissue Core for the Sidney Kimmel Cancer Center (SKCCC) at Johns Hopkins School of Medicine, utilizing stringent protocols to assess and quantify antibody staining, we have developed an anti-CD206 reagent to allow staining of human tissue microarrays to assess M2-TAM infiltration (28, 29, and submitted). Utilizing this antibody, we have demonstrated a significant increase in M2-TAMs in prostate tumors compared to normal tissue.

We will also quantify the extent of CD8+ T cell and CD4+ T cell infiltration into the prostate from harvested prostate glands of treated patients. We will quantify markers of apoptosis in prostate tumor specimens of treated patients using TUNEL staining and expressed as the mean staining percentage in tumor tissue and quantify markers of cell proliferation in prostate tumor specimens of treated patients using Ki-67 staining and expressed by the mean staining percentage in tumor. We will evaluate the proportion of pathological complete responses in prostate tumor specimens of treated patients who achieve an undetectable PSA (<0.1 ng/mL) by 2 months after prostatectomy.

3. Patient Selection

3.1 **Target Population**

Subjects will include men with multifocal, Gleason 7 or greater, clinically localized prostate cancer (NCCN High Risk / Very High Risk) for whom the decision has been made to perform radical prostatectomy at Johns Hopkins Hospital. Subjects will be identified and recruited through the Outpatient Clinic of the Department of Urology and from the Multidisciplinary Prostate Cancer Clinic.

3.2 **Inclusion Criteria**

To be eligible for this study, patients must meet *all* of the following criteria:

- Histologically confirmed adenocarcinoma of the prostate (clinical stage T1c–T3b. • N0, M0) without involvement of lymph nodes, bone, or visceral organs

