Power. For the primary outcome of pre- vs. post-treatment decrease in M2-TAM infiltration, power is based on the paired t-test. With 20 patients, we have the power (\geq 81%) to detect a decrease of \geq 0.67 standard deviation unit (effect size = 0.67) (14). This is likely to be conservative as we observed a much larger difference in M2-TAM levels between primary and metastatic tumors in our data. Power calculated using PASS v. 11 (NCSS Software, Kaysville, UT). The continuous toxicity monitoring design with n=20 above has probability = 0.048 of early stopping if the Grade \geq 3 AE rate is <15%. Toxicity boundaries calculated using software developed by Ivanova (13)

(http://cancer.unc.edu/biostatistics/program/ivanova/ContinuosMonitoringForToxicity.aspx)

Frequency, types, and grades of adverse events in each treatment group will be measured using the NCI Common Toxicity Criteria version 4.0, and will be summarized using descriptive statistics. Formal safety assessments will be performed from the time of first administration Dupilumab until the 60th postoperative day.

10.1.2: **Early stopping rule for feasibility:** We do not anticipate an increase in the surgical difficulty with the use of neoadjuvant DUPILUMAB. Men who have had acute (post-biopsy) and prolonged issues (chronic prostatitis) with prostate infection/inflammation are fairly routine in urologic surgical practice, and we anticipate that the immune infiltrate potentially induced by DUPILUMAB would not pose a substantial increase in surgical difficulties. However, in addition to safety, feasibility will be monitored separately. The feasibility rule for this study will be based on a change in surgical outcomes beyond what may be expected for patients without presurgical interventions and that may be attributable to the study drug. These events would include: (1) average blood loss in excess of 2500 mL, (2) average operative time in excess of 3.5 hours, and (3) average hospital stay in excess of 4 days. These values are

approximately 2 standard deviations above the average surgical outcomes for men undergoing radical prostatectomy at Johns Hopkins Hospital.

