We require that the probability that the surgery will not be complicated by these events to be high (≥90%). We will monitor this endpoint after every patient. If it becomes apparent that the surgeries are being negatively impacted by the pre-surgical investigational treatments, then the study will be suspended for review. This stopping rule will halt enrollment if the posterior probability of no complications <0.90 is greater than 80%. The prior probability for this rule has a Beta-distribution with parameters of 9 and 1, based on the expectation that these treatments will not impact the feasibility of surgery. Instances where the study would be temporarily suspended are listed below.

Stopping rules:

- Not feasible if both of the first 2 patients have surgical complications.
- Not feasible if two of the first 3 patients have complications.
- Not feasible if 2 out of the first 4 patients have complications.
- Not feasible if 3 out of the first 6 patients have complications.
- Not feasible if 4 out of the first 8 patients have complications.
- Not feasible if 5 out of the first 10 patients have complications.
- Not feasible if 6 out of the first 12 patients have complications.
- Not feasible if 7 out of the first 14 patients have complications.
- Not feasible if 8 out of 16 patients have complications.

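### The feasibility cut-offs rest on prostatectomy patients of unstated risk group, and the no-drug event rate is never checked against the rule's own 10% limit

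*Combined protocol and SAP*

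**What the plan says.** Section 10.1.2 (early stopping rule for feasibility) says the rule looks for "a change in surgical outcomes beyond what may be expected for patients without presurgical interventions" that may also be attributable to the drug. The events are "1) average blood loss in excess of 2500 mL, (2) average operative time in excess of 3.5 hours", and "average hospital stay in excess of 4 days". These values are said to be "approximately 2 standard deviations above the average surgical outcomes for men undergoing radical prostatectomy at Johns Hopkins Hospital". No mean, SD, calendar period, surgical technique or risk group is given for that reference.

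The same section wants "the probability that the surgery will not be complicated by these events to be high", set at 90% or more. With a Beta(9,1) prior, enrolment halts if the posterior probability that the complication-free rate is below 0.90 exceeds 80%. The rule is checked after every patient, and a list of suspension counts follows. Crossing suspends the study for review.

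The synopsis describes men with at least NCCN high-risk disease. Section 3.1 describes "clinically localized prostate cancer (NCCN High Risk / Very High Risk) for whom the decision has been made to perform radical prostatectomy". The criteria in section 3.2 are looser: stage T1c to T3b, Gleason sum of 7 or more and at least 2 positive cores. They would admit some Gleason 7 men who meet none of the synopsis's high-risk conditions.

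**The concern.** This is a single-arm trial, so the historical cut-offs are the only comparator for surgical feasibility. They do their job only if untreated men like those enrolled would cross them well under 10% of the time. The plan gives no such rate, and its reference group is not tied to the trial's declared risk group.

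The error could run either way. If enrolled men have longer or bloodier operations than the reference group, the rule can suspend the study for a drug that does nothing. If their operations are easier, the rule can miss real harm. The counting rule itself has no risk adjustment and no attribution step.

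**Working it through.** **Inputs from section 10.1.2:** cut-offs at mean + 2 SD; limit of 10% complicated; Beta(9,1) prior; posterior threshold 0.80; monitoring after every patient. The sample size of 20 is from section 4.2. **Assumptions:** a man counts as complicated if he crosses any of the three cut-offs; a case-mix shift of *d* SD applies equally to all three outcomes. The documents give no value for *d*.

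**1. The plan's own list.** With *k* complications in *n* men, the posterior for the complication-free rate is Beta(9 + n − k, 1 + k), and the rule stops when Pr(rate < 0.90) > 0.80. The first three entries reproduce: 2/2 (0.910), 2/3 (0.889), 2/4 (0.866). From n = 6 the list departs from the criterion:

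| n | Smallest k meeting the criterion (posterior) | Printed k |
|---|---|---|
| 6 | 2 (0.816) | 3 |
| 8 | 3 (0.917) | 4 |
| 10 | 3 (0.885) | 5 |
| 12 | 3 (0.848) | 6 |
| 14 | 3 (0.807) | 7 |
| 16 | 4 (0.902) | 8 |

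Results are therefore given under both versions. The 2 SD statement cannot be reproduced, because no mean or SD is stated.

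**2. No-drug rate, normal outcomes, no shift.** Each cut-off: 1 − Φ(2) = 0.0228. Any of three: 2.3% if the events fully overlap; 1 − (1 − 0.0228)³ = 6.7% if independent; never more than 3 × 0.02275 = 6.8%. All are below 10%.

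**3. Shift that brings an inert drug to 10%.**
- Fully overlapping: 1 − Φ(2 − d) = 0.10 gives d = 0.72.
- Independent: 1 − Φ(2 − d)³ = 0.10 gives d = 0.18.
- Common correlation 0.3, 0.5 or 0.8: d = 0.22, 0.27 or 0.40.
- Only one of three independent outcomes shifts: d = 0.42.

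**4. Chance of suspension with an inert drug** (exact binomial recursion over 20 men; each range runs from fully overlapping to independent outcomes):

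| Assumed shift (SD) | Any-of-three rate | Posterior criterion | Printed list |
|---|---|---|---|
| 0 | 2.3–6.7% | 1.0–10.2% | 0.3–2.6% |
| 0.25 | 4.0–11.5% | 3.4–30.2% | 0.9–7.4% |
| 0.5 | 6.7–18.7% | 10.2–63.2% | 2.6–18.4% |
| 1.0 | 15.9–40.4% | 50.7–99.0% | 13.5–67.0% |

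At a true rate of exactly 10%, suspension has probability 23.1% under the criterion and 5.6% under the list.

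**5. Skewness, no shift.** Mean + 2 SD is not a fixed tail for right-skewed quantities. The tail is 4.98% for an exponential, 4.24% for a gamma with shape 4, and 4.45% and 4.05% for lognormals with log-SD 0.5 and 0.3. For three independent outcomes, 1 − (1 − 0.0405)³ = 11.7% and 1 − (1 − 0.0498)³ = 14.2%. With full overlap the rate stays at 4% to 5%. For a 4.5% tail with intermediate dependence (Gaussian copula), it is 10.8% at correlation 0.5 and 9.3% at 0.7.

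**The case against.** A reader might infer that high-risk case mix alone will push an inert drug over the limit. The documents do not support that. Nothing in them says that high-risk men bleed more, take longer in surgery or stay longer, so both the size and the direction of any shift are unknown. Reading the reference group as every prostatectomy patient is natural but not stated. Because section 3.2 admits some men who are not high risk, the enrolled group may also be closer to the hospital's general caseload than the synopsis suggests.

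The larger figures depend on unfavourable assumptions. The 12% to 14% result needs three independent skewed outcomes, yet blood loss, operative time and stay come from the same operation and are likely to be correlated. The 63% and 99% figures need independence, an assumed shift and the posterior criterion in place of the printed list.

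A reader might also infer that a crossing would end the trial or convict the drug. It would not: the study is suspended for review. The rule's stated target includes attribution to the drug, section 7.4 has the principal investigator and urologist co-investigators judge relatedness, and the monthly meetings in section 9.3 cover participant characteristics.

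All of this stands, and it limits the point. It does not supply the missing reference cohort or background rate, and the reviewers would need both to judge attribution.

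**Conclusion.** The point holds as a gap in calibration. The benchmark is not tied to the trial's declared risk group, and the no-drug rate of any of the three events is never compared with the 10% limit. A breach with an inert drug is possible, not demonstrated.

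The margin depends on dependence and shape. Normal outcomes with no shift stay within the limit; a shift of 0.18 to 0.72 SD, or skewed outcomes with weak dependence, would use it up. At an assumed 0.5 SD shift, false suspension is 10% to 63% under the posterior criterion and 3% to 18% under the list. These results assume a common shift and per-patient counting of any of the three events. Only the hospital's own data can say where in the range the trial lies.

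**What to change.** Take the reference distribution from the hospital's own prostatectomies in men who had no presurgical treatment and who match the trial's eligibility and risk definition. State the cohort, its period, and the observed per-patient rate of any of the three events. Confirm that this rate is below 10% before applying the rule. If it is not, re-derive the cut-offs from that series' empirical upper percentiles, because mean + 2 SD does not fix the tail of a skewed outcome.

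Three passages should be reconciled at the same time:
- the cut-offs are worded as averages, but complications are counted per patient;
- the printed list departs from the Beta(9,1)/80% criterion from n = 6;
- the section 3.2 criteria are looser than the risk group in the synopsis and section 3.1.

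The cost is one query of the surgical records and a wording change, with the possibility that the cut-offs move. It assumes that per-patient records exist, as the plan's reference to a hospital average and SD implies. No extra patients or procedures are needed.

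### From n=6 to n=16 the printed feasibility stopping list needs 1.33 to 2.33 times as many complications as the Beta(9,1)/80% criterion it is said to come from

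*Combined protocol and SAP*

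**What the plan says.** Section 10.1.2 of the combined protocol and SAP monitors surgical feasibility separately from toxicity. The aim is stated as "We require that the probability that the surgery will not be complicated by these events to be high", with 90% as the minimum. The rule is: "This stopping rule will halt enrollment if the posterior probability of no complications <0.90 is greater than 80" per cent. The prior is given too: "The prior probability for this rule has a Beta-distribution with parameters of 9 and 1". On timing: "We will monitor this endpoint after every patient". There is also a qualitative trigger for suspension pending review: "If it becomes apparent that the surgeries are being negatively impacted by the pre-surgical investigational treatments".

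The section then says "Instances where the study would be temporarily suspended are listed below" and prints nine lines under a heading that calls them stopping rules. The listed points are 2/2, 2/3, 2/4, 3/6, 4/8, 5/10, 6/12, 7/14 and 8/16 (complications/patients). Two of the lines read "Not feasible if 2 out of the first 4 patients have complications" and "Not feasible if 3 out of the first 6 patients have complications". No other prior, target or cut-off is given for this rule.

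**The concern.** The criterion and the list are presented as one rule, but they give different decisions. From n=4 onward every listed point is exactly half of the patients. That is a surprising boundary for a rule meant to protect a 90% uncomplicated rate and starting from a prior with mean 9/(9+1) = 0.90.

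A team that treats the list as the boundary would keep enrolling in situations where the stated criterion says to suspend. With 4 complications in 10 patients, for instance, the posterior probability that the uncomplicated rate is below 0.90 is 0.965. Feasibility is a secondary objective (Section 1.2), and this is the only quantitative rule that monitors it.

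**Working it through.** **Inputs, all from Section 10.1.2:** prior Beta(9,1) on the probability p of uncomplicated surgery; target 0.90; suspend if Pr(p < 0.90 | data) > 0.80; look after every patient. The planned size of 20 is from Section 4.2.

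**Formula.** With x complications in n patients, the posterior for p is Beta(9+n−x, 1+x). Because the parameters are integers, Pr(p < 0.90) = Pr(Y ≤ x) with Y ~ Binomial(n+9, 0.10).

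**Worked example, 2/4.** Y ~ Binomial(13, 0.10), and Pr(Y ≤ 2) = 0.254 + 0.367 + 0.245 = 0.866. This exceeds 0.80. With x=1 it is 0.621, so 2 is the minimum and the listed entry is reproduced.

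**All nine looks:**

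| n | Listed | Criterion minimum | Ratio | Posterior at criterion minimum | Posterior at listed count | Posterior one below listed count |
|---|---|---|---|---|---|---|
| 2 | 2 | 2 | 1.00 | 0.910 | 0.910 | 0.697 |
| 3 | 2 | 2 | 1.00 | 0.889 | 0.889 | 0.659 |
| 4 | 2 | 2 | 1.00 | 0.866 | 0.866 | 0.621 |
| 6 | 3 | 2 | 1.50 | 0.816 | 0.944 | 0.816 |
| 8 | 4 | 3 | 1.33 | 0.917 | 0.978 | 0.917 |
| 10 | 5 | 3 | 1.67 | 0.885 | 0.991 | 0.965 |
| 12 | 6 | 3 | 2.00 | 0.848 | 0.997 | 0.986 |
| 14 | 7 | 3 | 2.33 | 0.807 | 0.999 | 0.994 |
| 16 | 8 | 4 | 2.00 | 0.902 | 0.9995 | 0.998 |

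At the last six looks the posterior one complication below the listed number is already above 0.80. For every n, the criterion's minima are 2 for n=2–6, 3 for n=7–14 and 4 for n=15–20.

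**Could another cut-off explain the list?** With this prior and target, suspending at 2/4 needs a cut-off below 0.866. Not suspending at 7/16 needs a cut-off of at least 0.998. No value does both.

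**Chance of suspension by patient 20.** This is an exact binomial recursion that assumes one independent yes/no event per patient.

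| True complication rate | List, its nine looks only | List, last count carried forward to unlisted n | Criterion, same nine looks | Criterion, every patient |
|---|---|---|---|---|
| 10% | 0.06 | 0.09 | 0.20 | 0.23 |
| 20% | 0.21 | 0.29 | 0.60 | 0.68 |
| 30% | 0.43 | 0.56 | 0.87 | 0.92 |
| 40% | 0.66 | 0.81 | 0.97 | 0.99 |

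With the looks held the same, the gap at 20% is 0.21 against 0.60, so boundary height rather than look frequency accounts for most of it.

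The two rules are identical through patient 4, with suspension probabilities 0.052, 0.181, 0.348 and 0.525 at the four rates. Given no suspension by then, the chance of a later one (list at its own looks against criterion after every patient) is 0.004 vs 0.19, 0.03 vs 0.61, 0.12 vs 0.88 and 0.28 vs 0.98.

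**The case against.** The best defence is that the list is only illustrative. It is introduced as instances, every listed point does satisfy the criterion (the lowest posterior is 0.866), and it has no entry for n=5, 7, 9, 11, 13, 15 or 17–20, so it cannot by itself deliver monitoring after every patient. On that reading the criterion governs and nothing is contradicted.

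The reading is possible but not the natural one. The heading and the wording of each line present decision rules. The first three entries are the exact minima, which is what a boundary table shows, and examples would hardly switch to half of all patients thereafter. Even as examples, the list leaves the operative boundary from n=5 onward unprinted and misleads about where it lies from n=6.

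Several smaller points stand. The minima at 2/6 (0.816) and 3/14 (0.807) are close to the cut-off; without those two looks the ratios run from 1.33 to 2.0. Carrying the last listed count forward to unlisted n narrows the gap (0.29 against 0.68 at a true 20% rate) but does not close it. The three events are written as averages and tied to attribution to study drug, so the suspension probabilities are illustrative until a per-patient event is defined.

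The consequence is also bounded. Suspension is temporary and for review, a qualitative trigger exists, and perioperative recording (7.4), monthly meetings (9.3) and ongoing review (11.5) continue.

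**Conclusion.** The concern holds. The printed list does not follow from the stated prior, target and cut-off at six of its nine looks, and no alternative cut-off rescues it. Used as a boundary, it gives little further protection once patient 4 has passed without suspension.

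The boundary comparison rests only on figures printed in Section 10.1.2 and on counting complications per patient. The suspension probabilities also assume independent binary events at a constant rate. The primary analysis and the Grade 3 or higher toxicity boundaries are not affected. This should be fixed, but it does not threaten the trial's main result.

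**What to change.** State in Section 10.1.2 which part governs, and make the other agree. There are two coherent options:

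- **The criterion governs.** Replace the list with the boundaries it yields for every n: 2 of the first 2–6, 3 of the first 7–14, 4 of the first 15–20. The price is more suspensions when surgery is going acceptably: 0.23 rather than 0.06 at a true 10% rate. At an assumed 6.7% rate (any of three independent events beyond 2 SD under a normal tail) it is 0.10 rather than 0.03.
- **The list governs.** Withdraw the Beta(9,1) prior, the 80% cut-off and the 90% requirement as its basis, and say what happens at the unlisted n. The price is lower sensitivity: a 0.21 rather than 0.68 chance of suspension at a true 20% rate.

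Either way, print the operating characteristics of the chosen rule. Also reword the three events, now expressed as averages, as events that can be scored yes or no for each patient, since both versions of the rule count patients. The whole change is one list, one sentence and three reworded definitions, with no new data.

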10.2.2 Analysis of the secondary endpoints

The secondary endpoints of this study have previously been defined (see Section 8.3). The statistical analysis of these endpoints is described below. Data transformation will be performed when they are not normally distributed.

- **Apoptotic markers.** The primary efficacy objective of this study is to observe an anti-tumor effect consistent with the agent's proposed mechanism of action (MOA), antibody-dependent cellular cytotoxicity (ADCC). Tumor cell death will be quantified by TUNEL staining, Caspase 3 staining, and FcGamma staining and will be expressed as the mean staining percentage in tumor samples. Standard deviations, 95% confidence intervals, and ranges will also be reported where appropriate. Means will be compared pre-treatment (from pre-treatment biopsies) vs. post-treatment using two-way analysis of variance (ANOVA).
- **Proliferation markers.** Ki-67 staining will be expressed as the mean staining percentage in tumor samples. Standard deviations, 95% confidence intervals, and ranges will also be reported where appropriate. Means will be compared pre-treatment vs. post-treatment using two-way ANOVA.
- CD8⁺ T cell infiltration. Mean CD8⁺ T cell staining percentage in harvested prostate tissues will be reported. The standard deviation, 95% confidence interval, median, and range of values will also be reported where appropriate. Since the CD8⁺ T cell quantity is a ratio variable and the distribution is skewed, the log transformation will be used for the analysis. Tissue microarrays (TMAs) using the highest-grade/largest tumor per patient and sampling it with 100-fold redundancy will be used for CD8⁺ T cell quantification. We expect that 3-50% of the spots per patient will be assigned a carcinoma diagnosis by the study

pathologist. Cores with both tumor and normal tissue will be excluded if they contain >10% of the other component. The percent positive staining score for $CD8^+$ T cells in the spots classified as tumor will be used to quantify the outcome. The mean will be used to pool multiple spot measurements for each patient..

- **Regulatory T cell (T_{reg}) density**. The methods for analyzing T_{reg} infiltration will be similar to those described for CD8⁺ T cell infiltration. Descriptive statistics and graphical summaries will be provided. In addition, the CD8⁺/T_{reg} ratio and the CD4⁺/T_{reg} ratio will be computed, and reported using descriptive statistics.
- **CD4⁺ T cell density.** The methods for quantifying and analyzing CD4⁺ T cell infiltration will be similar to those described for CD8⁺ T cell infiltration. Descriptive statistics and graphical summaries will be provided.
- Pathological complete responses (pCR). This will be defined as an absence of tumor identification on standard histological analysis of the resected prostate specimens.
- **PSA response rates**. This will be defined as an undetectable PSA (<0.1 ng/mL) at 3 months after prostatectomy. The proportion of patients achieving a PSA response will be compared between treatment arms using the Mantel-Haenszel test.
- Time to PSA recurrence. This will be defined as the interval from prostatectomy to the time when the serum PSA is ≥0.2 ng/mL. For subjects who have not yet demonstrated PSA recurrence at the time of censoring, patients will be censored at the date of the last assessment that shows a lack of PSA recurrence. For each treatment arm, the median time to PSA recurrence after prostatectomy (*i.e.*, the median PSA-recurrence-free survival) will be estimated with 95% confidence intervals using Kaplan-Meier survival analysis. Comparisons will be sought using the log-rank test, stratified by Gleason score.

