- Administration of Dupilumab days 1, 8, 15, 22, 29, 36, 43
- Interval history and focused physical examination (including vital signs before and 1 hour post subcutaneous injection)

On day 57:

- Medical history and focused physical examination (including vital signs)
- Review of medications
- Performance status
- Adverse events/toxicity evaluation
- Hematology and chemistry laboratories, as clinically indicated
- Serum PSA
- Radical prostatectomy
- Pathologic review of surgical specimen according to standard procedures
- Evaluation of harvested prostate gland for secondary endpoints

Post-operative day 30 and day 60:

- Performance status
- Adverse events/toxicity evaluation
- PSA every 3 months (post-op year 1), then every 6 months (post-op years 2-3)

Criteria for Primary endpoint:

evaluation • A comparison of pre-dupilumab M2-TAM infiltration in the biopsy vs. post-dupilumab M2-TAM infiltration in the RP specimen

Secondary endpoints:

- Frequency, type, and severity of adverse events
- M2-TAM infiltration in the RP specimen
- Quantify the extent of CD8+ T cell infiltration into the prostate from harvested prostate glands of treated patients
- Quantify the extent of CD4+ T cell and Treg infiltration into the prostate in prostate specimens of treated patients
- Quantify markers of apoptosis in prostate tumor specimens of treated patients using TUNEL staining and expressed as the mean staining percentage in tumor tissue
- Quantify markers of cell proliferation in prostate tumor specimens of treated patients using Ki-67 staining and expressed by the mean staining percentage in tumor
- Evaluate the proportion of pathological complete responses in prostate tumor specimens of treated patients

Evaluate PSA response rates defined as the proportion of patients who achieve an undetectable PSA (<0.1 ng/mL) by 2 months after prostatectomy.

Statistical For the primary outcome: pre- and post-treatment M2-TAM infiltration will be compared using a paired t-test, or nonparametric signed rank test if data don't conform to a Gaussian distribution. Power is based on the paired t-test. With 20 patients, we have the power (≥ 81%) to detect a decrease of ≥0.67 standard deviation unit (effect size = 0.67) (14). This is likely to be conservative as we observed a much larger difference in M2-TAM levels between primary and metastatic tumors in our data. Power calculated using PASS v. 11 (NCSS Software, Kaysville, UT).

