1.2 Secondary Objectives

- To evaluate the safety and tolerability of DUPILUMAB administered 600 mg s.q. on day 1, and then 300 mg s.q. on days 8,15, 22, 29, 36, 43. They will then undergo surgery on day 56.
- To evaluate the feasibility of administering DUPILUMAB administered 600 mg s.q. on day 1, and then 300 mg s.q. on days 8,15, 22, 29, 36, 43.
- Quantify the extent of CD8+ T cell infiltration into the prostate from harvested prostate glands of treated patients
- Quantify the extent of CD4+ T cell and Treg infiltration into the prostate in prostate specimens of treated patients
- Quantify markers of apoptosis in prostate tumor specimens of treated patients using TUNEL staining and expressed as the mean staining percentage in tumor tissue
- Quantify markers of cell proliferation in prostate tumor specimens of treated patients using Ki-67 staining and expressed by the mean staining percentage in tumor
- Evaluate the proportion of pathological complete responses in prostate tumor specimens of treated patients
- Evaluate PSA response rates defined as the proportion of patients who achieve an undetectable PSA (<0.1 ng/mL) by 2 months after prostatectomy.

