2.2 Treatment Background

2.2.1 Study Agent (DUPILUMAB) Background

Dupilumab is a human monoclonal IgG4 antibody that inhibits interleukin-4 (IL-4) and interleukin-13 (IL-13) signaling by specifically binding to the IL-4R α subunit shared by the IL-4 and IL-13 receptor complexes. Dupilumab inhibits IL-4

signaling via the Type I receptor and both IL-4 and IL-13 signaling through the Type II receptor (11, 12).

Blocking IL-4R α with dupilumab inhibits IL-4 and IL-13 cytokine-induced responses, including the release of proinflammatory cytokines, chemokines and IgE

Dupilumab is produced by recombinant DNA technology in Chinese Hamster Ovary cell suspension culture.

DUPILUMAB (dupilumab) Injection is supplied as a sterile, preservative-free, clear to slightly opalescent, colorless to pale yellow solution for subcutaneous injection. DUPILUMAB is provided as a single-dose pre-filled syringe with or without needle shield in a 2.25 mL siliconized Type-1 clear glass syringe. The needle cap is not made with natural rubber latex. Each pre-filled syringe delivers 300 mg dupilumab in 2 mL which also contains L-arginine hydrochloride (10.5 mg), L- histidine (6.2 mg), polysorbate 80 (4 mg), sodium acetate (2 mg), sucrose (100 mg), and water for injection, pH 5.9.

Mechanism of Action

Dupilumab is a human monoclonal IgG4 antibody that inhibits interleukin-4 (IL-4) and interleukin-13 (IL-13) signaling by specifically binding to the IL-4R α subunit shared by the IL-4 and IL-13 receptor complexes. Dupilumab inhibits IL-4 signaling via the Type I receptor and both IL-4 and IL-13 signaling through the Type II receptor.

Blocking IL-4R α with dupilumab inhibits IL-4 and IL-13 cytokine-induced responses, including the release of proinflammatory cytokines, chemokines and IgE.

Pharmacodynamics

Consistent with receptor blockade, serum levels of IL-4 and IL-13 were increased following dupilumab treatment. The relationship between the pharmacodynamic activity and the mechanism(s) by which dupilumab exerts its clinical effects is unknown.

Pharmacokinetics

Absorption

Following an initial subcutaneous (SC) dose of 600 mg, dupilumab reached peak mean \pm SD concentrations (Cmax) of 70.1 \pm 24.1 mcg/mL by approximately 1 week post dose.

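### The apoptosis endpoint is TUNEL alone in the objectives but three unranked stains in Section 10.2.2, and Section 8.3, cited as its definition, has no apoptosis entry

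*Combined protocol and SAP*

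**What the plan says.** Section 1.2 lists as a secondary objective: "Quantify markers of apoptosis in prostate tumor specimens of treated patients using TUNEL staining and expressed as the mean staining percentage in tumor tissue". The synopsis has the same content in its rationale, its objectives and its endpoint list, and Section 2.3.3 repeats it: "We will quantify markers of apoptosis in prostate tumor specimens of treated patients using TUNEL staining". TUNEL is the only stain named in any of these places.

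Section 10.2.2, under apoptotic markers, has a different list: "Tumor cell death will be quantified by TUNEL staining, Caspase 3 staining, and FcGamma staining". Each stain is to be expressed as a mean staining percentage and compared before and after treatment. The section does not rank the stains, combine them or adjust for there being three. Section 10.5.3 sends the reader to Section 10.2 for the methods, so this is the operative text.

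For definitions, Section 10.2.2 points elsewhere: "The secondary endpoints of this study have previously been defined (see Section 8.3". Sections 8.3.1 to 8.3.8 cover adverse events, Ki-67, CD8, Treg, CD4, pathological complete response, PSA response and time to PSA recurrence. None covers apoptosis, and no assay is described for TUNEL, Caspase 3 or FcGamma.

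The apoptosis bullet opens by describing an anti-tumor effect "consistent with the agent's proposed mechanism of action (MOA), antibody-dependent cellular cytotoxicity (ADCC". Section 2.2.1 describes a drug that "inhibits interleukin-4 (IL-4) and interleukin-13 (IL-13) signaling by specifically binding to the IL-4R α subunit".

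**The concern.** A reader who follows the objectives expects one apoptosis result. A reader who follows the methods section obtains three, and nothing says which of them answers the objective. If the stains disagree, the plan does not say whether apoptosis changed.

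FcGamma adds a separate problem. It occurs once in the documents, without a definition, directly after a mechanism that the drug background does not describe. Under 10.2.2 as written, a change in FcGamma staining would be reported as a change in tumor cell death, although no part of the plan explains the link.

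At stake are the interpretation of one secondary endpoint and its false-positive rate. The synopsis makes future studies depend on M2-TAM reduction, feasibility and safety, so no stated decision turns on apoptosis.

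**Working it through.** **1. The plan's own figure.** The only efficacy power stated is for the primary endpoint: at least 81% with 20 pairs and an effect size of 0.67. For a two-sided paired t-test at 0.05, the degrees of freedom are 19 and the noncentrality is 0.67 × √20 = 3.00. The noncentral t distribution gives power of 81.1%, so the figure reproduces. The point below does not touch it. The plan states no figure for the apoptosis endpoint.

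**2. The definitions side by side.**

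| Place | Stains named for apoptosis |
|---|---|
| Synopsis (rationale, objectives, endpoint list) | TUNEL |
| 1.2 Secondary Objectives | TUNEL |
| 2.3.3 Rationale for immunobiologic endpoints | TUNEL |
| Study calendar footnote f; 10.3.1 | apoptosis mentioned, no stain |
| 8.3.1 to 8.3.8 | no apoptosis entry |
| 10.2.2 | TUNEL, Caspase 3, FcGamma |

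The cross-reference from 10.2.2 to 8.3 cannot settle the difference, because 8.3 has nothing on the subject. By contrast, 8.3 does give staining methods for Ki-67, CD8, CD4 and FoxP3.

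**3. FcGamma.** Its only context is the cytotoxicity mechanism in the preceding sentence. That sentence conflicts with Section 2.2.1 on mechanism. It also calls this effect the primary efficacy objective, whereas Section 1.1 makes M2-TAM infiltration primary. Deleting the mechanism sentence alone would leave FcGamma listed as a cell-death measure with no rationale at all.

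**4. False-positive rate.** Section 10.5.1 sets significance at P ≤ 0.05 and states no multiplicity adjustment. For k independent tests with no true effect, the chance of at least one significant result is 1 − 0.95^k:

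- k = 1: 5.0%
- k = 2 (TUNEL and Caspase 3): 1 − 0.9025 = 9.75%
- k = 3: 1 − 0.857375 = 14.3%

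The documents give no correlation between stains, so a range is assumed. The results below come from simulating two-sided paired t-tests with 20 pairs, using 40,000 simulated trials per setting:

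| Assumed correlation | Two stains | Three stains |
|---|---|---|
| 0.3 | 9.6% | 13.2% |
| 0.5 | 9.1% | 12.8% |
| 0.8 | 7.8% | 10.4% |

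The simulation at zero correlation gave 14.4% for three stains, in line with the formula. Across the assumed range, three stains give at least twice the nominal 5%.

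**The case against.** The strongest reply is that Section 10.2.2 commits to all three stains, each with a mean and, where appropriate, a standard deviation, confidence interval and range. A reader might infer that the investigators may take the apoptosis result from whichever stain moves. The text does not support that: it plans three reported measures and offers no choice among them. What stands is narrower. No lead marker is named, and the list differs from the objectives. The plural used for markers in the objectives does not close the gap, because TUNEL is the only one they name.

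A reader might also infer that FcGamma does not measure cell death. The documents never say what the stain measures, and 10.2.2 itself lists it under cell death, so the stronger statement would rest on outside knowledge. What the documents do show is that the stain is undefined and its link to cell death is unexplained.

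Third, 14.3% is the value under independence. It is not a fixed rate, and stains intended to measure the same process would probably be positively correlated, which lowers it. Nor is it a strict ceiling: the general bound is 3 × 5% = 15%. Section 10.5.1 also says that most outcomes will be reported descriptively, and the plan adjusts no secondary biomarker for multiplicity. Naming one apoptosis stain would therefore not control error across the whole secondary set. All of this is correct and limits the weight of the figure, but it does not remove the conflict over what the endpoint is.

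**Conclusion.** The concern holds as a conflict of definition. The objectives give one stain, the methods section gives three without a lead marker, and the section cited as the definition is silent. The documents provide no basis for reporting FcGamma as tumor cell death.

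The chance of at least one false positive for this endpoint is 14.3% if the three tests are independent and about 10% to 13% at assumed correlations of 0.8 to 0.3, against 5% for one named stain. These figures assume no true effect, two-sided tests (the plan does not state sidedness) and no adjustment; the correlations are assumptions.

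Severity is low. This is a secondary endpoint in a 20-patient single-arm study, and the stated power for the primary endpoint reproduces and is unaffected.

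**What to change.** - In 10.2.2, define the apoptosis endpoint as TUNEL mean staining percentage, as in 1.2.
- Add the same definition to 8.3, with the assay description, so that the cross-reference leads somewhere.
- Label Caspase 3 as supportive.
- Remove FcGamma from the measures of tumor cell death. If the sponsor wants the data, keep it as a separately labelled exploratory marker and say what it is meant to show.

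The cost is a sentence or two in 10.2.2 and a short entry in 8.3. The downside is that Caspase 3 and FcGamma results no longer count toward the apoptosis endpoint. With one named stain, the false-positive rate for this endpoint returns to 5%.

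One related matter stays open unless it is settled in the same edit. Section 10.1 plans paired t-tests for the secondary biomarkers, while 10.2.2 compares pre-treatment "vs. post-treatment using two-way analysis of variance (ANOVA"). The two give the same pre-post test only if patient is the second factor and there is one value per patient and time, which the plan does not state.
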